**IV. STUDY TIME FRAME:**

Proposal Development/Approval:	September 2020 - IRB Approval
Data Collection:	IRB Approval – June 2022
Data Cleaning and Analysis:	June 2022 – June 2023
Manuscript Preparation:	June 2023 – December 2023
Abstract Submission:	February 2023

**V. PUBLICATION AND PRESENTATION OF DATA:**

Data from this research study will be considered for submission to The Journal of Burn Care and Research, The Journal of the American Medical Association, the American Journal of Surgery, The American Surgeon, or other journal felt appropriate for publication. In addition, data from this research study may be submitted for presentation at the Annual Meeting of the American Burn Association, the Midwest Region Burn Conference, the Kansas Chapter of the American College of Surgeons, the Southwestern Surgical Congress Annual Meeting, and/or other meeting(s) as felt appropriate for the material.

**VI. STATISTICAL ANALYSIS:**

The data that is collected will be compiled, evaluated and summarized by calculating means and standard deviations for continuous data, medians and quartiles for ordinal data, and proportions for discrete data. One-way analysis of variance will be utilized to compare continuous data. Where heterogeneity of variance is identified, data will be either transformed and analyses rerun, or data will be analyzed using the Mann-Whitney U-Test. Chi-square analysis will be utilized for comparison of categorical data. Ordinal data will be analyzed using the Mann Whitney U-Test. Logistic regression analyses will be utilized to identify independent predictors of the outcomes variables of interest. All analyses will be run as two-tailed tests and results of analyses will be considered significant if the resultant P-value is less than or equal to 0.05. Analyses will be run using SPSS 19.0.

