### **II. STUDY OBJECTIVE:**

Evaluate the impact of HAT therapy versus placebo in the treatment of patients with an acute NSTI and sepsis.

Primary outcome:

1. Hospital survival (including those who die within 24 hours of hospital admission)

Secondary outcomes:

1. Duration of vasopressor therapy
2. Requirement for renal replacement therapy in patients with Acute Kidney Injury (AKI)
3. ICU length of stay (LOS)
4. Change in serum procalcitonin (PCT) over first 72 hours
5. Change in SOFA score over first 72 hours (measured as SOFA score daily for four days, with day one being admission, then 3 days after, totaling 4 days of treatment with HAT)
6. Procalcitonin clearance (formula = initial PCT – 72 hour PCT divided by initial PCT x 100)
7. Number of wound related surgeries
8. Wound status at time of hospital discharge:
  - a. Open
  - b. Closed

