**Variables collected will include:**

- Patient name
- Medical record number (FIN)
- Date of birth
- Date and time of diagnosis of NSTI
- Date and time of randomization
- Time from diagnosis of NSTI and sepsis to initiation of HAT: hours.
- Time on pressors prior to initiation of HAT: hours
- Patient demographics (age, gender)
- Location of NSTI infection
  - Perineum
  - Genitalia
  - Groin
  - Lower extremity
  - Upper extremity
  - Hand
  - Foot
  - Head/Neck
  - Back
  - Chest
  - Abdomen
  - Multiple/Other – free text
- Preexisting conditions – similar to [name] study:
  - None
  - Diabetes mellitus
  - Hypertension
  - Heart failure
  - Malignancy
  - Chronic obstructive pulmonary disease
  - Cirrhosis
  - Cerebrovascular accident
  - Acute Kidney Injury (AKI)
  - Chronic kidney disease
  - Morbid obesity (weight and height)
  - Immunocompromised (HIV infection, neutropenia, post-transplantation, other)
  - Active medical systemic steroid use at baseline
  - Illicit drug use evident by patient history or drug screen
  - Active tobacco or nicotine product use
- Time from diagnosis of NSTI to surgery: hours

- Total number of visits to the operating room for NSTI-related surgical intervention
- Identification of NSTI derived from pressure-related injury
- Wound status at time of ICU discharge:
  - Open
  - Closed
- Duration of vasopressor therapy: hours cumulative from entire hospitalization
- Positive blood cultures (Y/N)
- Organism present on wound culture
- Time to antibiotic use
- Antibiotic used
- Requirement for renal replacement therapy in patients with AKI (Y/N)
- Procalcitonin level daily for 4 days (with day one being admission/enrollment, then 3 days after, totaling 4 days of treatment with HAT)
- Daily SOFA score for 4 days (with day one being admission/enrollment, then 3 days after, totaling 4 days of treatment with HAT)
- Total ventilator days
- ICU LOS: Days
- Hospital length of stay: Days
- Discharge disposition: alive or deceased
- If the patient withdrew: Y/N
- Reason for patient withdrawal: Free text

Population:

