omitting HAT has not been formally studied in this population. Finally, the treatment duration in our study will be limited (i.e. a maximum of 4 days for vitamin C and thiamine and 7 days plus a 3 day taper for hydrocortisone).

The potential risks due to septic shock from a NSTI itself are expected to be no different for patients whether they are enrolled in this study or not.

Evaluations During Treatment:

The evaluation period will begin at the time HAT or placebo is initiated after sepsis criteria is met and end at hospital discharge.

The investigators will collect data as outlined above under “Data Collection.”

Subject Non-evaluability:

Subjects will be deemed non-evaluable and will be dropped from the study if they meet the exclusion criteria and/or elect to withdraw from the study.

Costs

Participants will never be charged for study-related drugs in this study, regardless of the group to which they are randomized. This means that participation in this study will not cost participants more or less than the cost of normal care. No charges for care other than those that would be normally received will be incurred during the study and the cost for participants' normal care will be the participants' and/or the participants' insurance provider's responsibility.

Participants will not be charged for the drugs used in this study. The pharmacy will be absorbing the costs of the drugs regardless of whether it's thiamine, vitamin C, hydrocortisone, or placebo.

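### Vasopressor hours and ICU days stop accruing at death, so under Section VI a mortality difference alone can shift both comparisons, in either direction

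*Combined protocol and SAP*

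**What the plan says.** Section II lists "Duration of vasopressor therapy" and "ICU length of stay (LOS") as secondary outcomes 1 and 3. The list of collected variables in Section III defines the first as "Duration of vasopressor therapy: hours cumulative from entire hospitalization" and the second simply as days.

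Section VI treats all continuous data alike: "One-way analysis of variance will be utilized to compare continuous data". Where variances are heterogeneous, "data will be either transformed and analyses rerun, or data will be analyzed using the Mann-Whitney U-Test". No test for heterogeneity is named.

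Death is mentioned in only two relevant places. The primary outcome is "Hospital survival (including those who die within 24 hours of hospital admission"), and the data fields include "Discharge disposition: alive or deceased". The paragraph on subject non-evaluability says "Subjects will be deemed non-evaluable and will be dropped from the study if they meet the exclusion criteria", or if they withdraw; it does not mention death.

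Section VII plans for mortality of 20% in controls and 4.24% with HAT, with 66 patients per arm.

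**The concern.** Both outcomes stop accumulating when a patient dies. A patient who dies on day 1 has a short ICU stay, and a patient who dies after prolonged support has many vasopressor hours. Neither value says how fast that patient was recovering.

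If HAT changes mortality, the arms contain different mixes of survivors and deaths. Preventing early deaths would make HAT appear to lengthen ICU stay. Preventing deaths that follow long vasopressor use would make HAT appear to speed weaning, although survivors recover no faster. The distortion is largest when the trial succeeds on its primary outcome. What is at stake is the reading of two named secondary outcomes.

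**Working it through.** **What the plan implies for deaths.** The vasopressor field counts hours over the whole hospitalization, the non-evaluability paragraph does not remove deaths, and Section VI compares the values recorded. Together these put every patient in with the total accrued up to death. For ICU days the same follows by implication only.

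**Inputs from the plan.** Mortality 20% and 20% x (1 - 0.788) = 4.24%; 66 per arm; two-sided testing at 0.05. The stated sample size reproduces: the pooled two-proportion formula without continuity correction gives 67 per arm, and 66 per arm gives 79.9% power. Expected deaths are 66 x 0.20 = 13.2 in controls and 66 x 0.0424 = 2.8 with HAT.

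**Formula.** Suppose HAT changes duration neither in survivors nor in those who die. Then:

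mean difference (HAT minus control) = (0.20 - 0.0424) x (survivor mean - mean in deaths) = 0.1576 x (survivor mean - mean in deaths).

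It is positive if deaths have shorter totals than survivors, negative if longer, and zero if mortality or the two means are equal.

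**Assumptions for size.** The documents give no durations, so all of the following are assumed.
- ICU days are lognormal with log-SD 0.7 (mean = median x 1.278) and a survivor median of 8 days, so a survivor mean of 10.22.
- Vasopressor hours are zero if untreated, otherwise lognormal with log-SD 0.8 (mean = median x 1.377). All patients who die are treated.
- The stepwise rule is ANOVA unless Levene's test has p <= 0.05, then Mann-Whitney.

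Rejection below means p <= 0.05 in the stated direction. Nominal is 2.5%, but this rule itself gives only about 1.2% to 1.5% per direction when nothing differs.

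**ICU stay, 20% versus 4.24%**

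| Median stay in deaths | Mean difference (days) | Rejection, stepwise rule |
|---|---|---|
| 1 day | 0.1576 x (10.22 - 1.28) = +1.41 | 17.6%, HAT longer |
| 2 days | 0.1576 x (10.22 - 2.56) = +1.21 | 13.2%, HAT longer |
| 5 days | 0.1576 x (10.22 - 6.39) = +0.60 | 4.6%, HAT longer |
| 8 days | 0 | 1.4% |
| 12 days | 0.1576 x (10.22 - 15.33) = -0.81 | 4.5%, HAT shorter |

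Using a log transformation instead of Mann-Whitney after the trigger gives 19.2%, 14.1%, 5.0%, 1.6% and 5.0%.

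**Vasopressor hours, 20% versus 4.24%**

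| Survivors treated, median | Median in deaths | Mean difference (hours) | Rejection, larger tail |
|---|---|---|---|
| 60%, 36 h | 12 h | +2.1 | 1.6% |
| 60%, 36 h | 18 h | +0.8 | 1.4% |
| 60%, 36 h | 36 h | -3.1 | 4.8%, HAT shorter |
| 60%, 36 h | 72 h | -10.9 | 13.3%, HAT shorter |
| 90%, 48 h | 12 h | +6.8 | 7.9%, HAT longer |
| 90%, 48 h | 18 h | +5.5 | 5.5%, HAT longer |
| 90%, 48 h | 36 h | +1.6 | 1.8% |
| 90%, 48 h | 72 h | -6.3 | 4.5%, HAT shorter |

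Example, fourth row: survivor mean 0.6 x 36 x 1.377 = 29.7 h; mean in deaths 72 x 1.377 = 99.2 h; 0.1576 x (29.7 - 99.2) = -10.9 h.

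**Smaller mortality difference.** With ICU deaths at a median of 2 days, 20% versus 15% gives about 3.5% under the stepwise rule. Equal mortality brings the rate back to the rule's own baseline.

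**The case against.** The strongest reply is that the plan is not silent. Its field definition and non-evaluability paragraph imply a default, namely totals as accrued for all patients. As a measure of resource use, time until death is a valid value. This stands: a reader might infer that deaths have no place in the analysis at all, and the documents do not support that. What is missing is a statement of what the resulting comparison means.

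A second reply is that nothing in the plan says either outcome will be read as recovery. That is also true. The reading is a risk rather than a stated intention. Section I does cite vasopressor weaning among the favourable results of the earlier before-after study, so the risk is not remote, although it adds that later randomized trials did not replicate those benefits.

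Third, the larger figures depend on assumptions. A reader might take the primary outcome's wording to mean that early deaths are expected. It says only that deaths within 24 hours count, and gives no information on timing. A reader might also quote Mann-Whitney applied in every trial, which for ICU stay gives 32.7% and 25.6% with deaths at 1 and 2 days. That is not the plan's rule, under which the rates are roughly half as large. Three of the eight vasopressor scenarios fall below the nominal 2.5%.

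These replies limit the size and the wording of the point. They do not remove the mechanism, which is algebraic.

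**Conclusion.** The point holds in limited form. Following the plan as written, a mortality difference alone shifts the comparisons of vasopressor hours and ICU days, in a direction set by whether deaths have shorter or longer totals than survivors. At the planned mortality the chance of a spurious one-direction finding ranges from no excess over the rule's baseline to about 18%, depending on durations that the documents do not give and on Levene's test as the assumed trigger. Confidence is high in the formula and low in any particular rate. If the true mortality difference is small, as the later trials cited in Section I make plausible, the effect is minor. It would be wrong to infer that the primary outcome or the sample size is compromised; neither uses these durations. This is a worthwhile, inexpensive clarification of two secondary outcomes.

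**What to change.** Add to Section VI:
- Vasopressor hours and ICU days will be reported by arm separately for survivors and for patients who died, beside in-hospital mortality. The survivor figures will be descriptive, without a p-value.
- The all-patient comparison of raw totals measures resource use and will not be used to claim faster or slower recovery.
- Optionally, a Mann-Whitney test with in-hospital death ranked worst may be added as a supportive analysis, labelled a composite of death and duration.

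The cost is two or three sentences and a few table rows. Durations and discharge disposition are already collected.

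There are two downsides. Survivors are not a fully randomized comparison: if the 15.76% of patients who live only because of HAT stay a median of 16 days instead of 8, a survivors-only test finds HAT longer in 13.3% (ANOVA) or 11.5% (Mann-Whitney) of trials. This is why those figures should carry no p-value. The composite is largely driven by mortality: from mortality alone it favours HAT in about 35% of trials at the planned rates, 16% at 20% versus 10%, and 7% at 20% versus 15%. It should therefore not be the main test.

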Patients will be enrolled within 24 hours of diagnosis of sepsis related to a NSTI. HAT will be initiated within 4 hours of enrollment (thus treatment with HAT can occur no later than 28 hours from diagnosis).

Per [name] original study, HAT consists of:

- 1) 1.5 g vitamin C every 6 hours for 4 days or until ICU discharge
- 2) 50 mg hydrocortisone every 6 hours for 7 days or until ICU discharge (followed by a taper over 3 days)
- 3) 200 mg thiamine every 12 hours for 4 days or until ICU discharge

In our study, due to the prolonged ICU course typical of most patients with NSTIs, it is not felt feasible to continue indefinitely "until ICU discharge." Thus, treatment will be continued for 4 to 7 days plus a 3 day taper (respectively) as above, with no plan for a longer duration of treatment.

The control arm will receive the same standard ICU care for NSTI but will not receive HAT. They will receive a placebo consisting of normal saline, indistinguishable to the treatment team (blinded) but known to the pharmacy team (unblinded to treatment and placebo groups). This is so that if the treatment team elects to give stress dose steroids, they can be administered without breaking protocol (i.e. if the patient is getting HAT, it includes steroids, so if the treating team wanted to start hydrocortisone - because they didn't know if the patient was on HAT or placebo and felt steroids were indicated - the pharmacist could ensure the patient was on steroids one way or another without unblinding the providers).

Duration of Study:

The study enrollment period will continue for one year after its initiation, or until enrollment goal is met. Patients will be followed until hospital discharge.

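### The 72-hour changes in SOFA and procalcitonin are compared between arms without baseline as a covariate, which gives up precision at almost no saving

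*Combined protocol and SAP*

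**What the plan says.** Section II lists eight secondary outcomes. Two are changes from a starting value: "Change in serum procalcitonin (PCT) over first 72 hours", and the corresponding change in SOFA, "measured as SOFA score daily for four days, with day one being admission". PCT clearance, the fall as a percentage of the initial value, is listed separately.

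The variable list in section III provides the starting values: "Daily SOFA score for 4 days (with day one being admission/enrollment" and "Procalcitonin level daily for 4 days (with day one being admission/enrollment".

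Section VI does not assign tests to outcomes. For continuous data, "One-way analysis of variance will be utilized to compare continuous data". Where variances are unequal, the data are transformed and retested or go to the Mann-Whitney test. For the remaining case, "Ordinal data will be analyzed using the Mann Whitney U-Test". The only regression named is logistic: "Logistic regression analyses will be utilized to identify independent predictors of the outcomes variables of interest".

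**The concern.** With two arms, one-way ANOVA is an unadjusted t-test, and the Mann-Whitney test is also unadjusted. Logistic regression does not fit a continuous change, and the plan presents it as a search for predictors, not as a comparison of arms. So whether SOFA change is treated as continuous or as ordinal, baseline enters only through the subtraction.

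Subtraction fixes the slope of the 72-hour value on baseline at 1. If the true slope is lower, as it commonly is, the raw change over-corrects for baseline and carries avoidable noise. ANCOVA estimates the slope instead.

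At stake is the width of the confidence intervals, and the power, for two secondary outcomes in a trial whose 132 patients were sized on mortality alone.

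**Working it through.** **The plan's own figure.** Section VII gives 66 per arm for mortality of 20% against 4.24%, two-sided 0.05, 80% power. The standard two-proportion formula without continuity correction gives 67 per arm, and power at 66 is 79.9%, so the figure reproduces. No figure is given for SOFA or PCT.

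**Inputs.** n = 66 per arm (section VII). Assumed, because the documents give neither: ρ, the correlation between the baseline and 72-hour values, and k, the 72-hour SD divided by the baseline SD.

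**Formulas**, in units of the baseline variance, for complete data:
- variance of raw change: 1 + k² − 2ρk
- residual variance under ANCOVA: k²(1 − ρ²)
- proportional variance cut: g = 1 − k²(1 − ρ²)/(1 + k² − 2ρk), which is (1 − ρ)/2 at k = 1
- narrowing of the confidence interval: 1 − √(1 − g)
- patients per arm that raw change would need for the same precision: 66/(1 − g)

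Example at k = 1, ρ = 0.5: g = 1 − 0.75/1 = 0.25; interval narrower by 1 − √0.75 = 13.4%; 66/0.75 = 88.0.

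**Results at equal SDs (k = 1):**

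| ρ | Variance cut | Interval narrower by | Equivalent n per arm |
|---|---|---|---|
| 0.3 | 35% | 19.4% | 101.5 |
| 0.5 | 25% | 13.4% | 88.0 |
| 0.7 | 15% | 7.8% | 77.6 |
| 0.8 | 10% | 5.1% | 73.3 |
| 0.9 | 5% | 2.5% | 69.5 |

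**Unequal SDs**, variance cut at ρ = 0.3, 0.5, 0.7:
- k = 0.7: 58%, 53%, 51%
- k = 1.3: 19%, 9%, 1%
- k = 1.5: 13%, 4%, 0.2%

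The gain vanishes as the slope ρk approaches 1. At k = 1.3, ρ = 0.7 the slope is 0.91 and g = 1 − (1.69 × 0.51)/(1 + 1.69 − 1.82) = 1 − 0.862/0.870 = 0.9%.

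**Mann-Whitney route, SOFA only.** This was simulated with 4,000 trials per setting and 66 per arm. Scores were integers from 0 to 24, with baseline mean 8, 72-hour mean 6 and baseline SD 3.5 (all assumed). The true effect was two standard errors of raw change. The comparator is Quade's rank analysis of covariance on baseline SOFA. Power at ρ = 0.3, 0.5, 0.7:
- k = 1: Mann-Whitney on raw change 47%, 46%, 45%; adjusted rank test 65%, 58%, 52%
- k = 1.3: 44%, 45%, 44% against 54%, 50%, 45%
- k = 0.7: 49%, 49%, 46% against 83%, 78%, 75%

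False-positive rates were 4.4% to 5.8%, and simulation error is about 0.8 percentage points at 50% power. PCT was not simulated on this route.

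**Missing 72-hour values.** Expected hospital deaths at the planning rates are 66 × 0.20 = 13.2 in the control arm and 66 × 0.0424 = 2.8 on HAT. These are expectations, not ceilings: at a true rate of 20%, more than 13 deaths among 66 occur about 45% of the time. The documents do not say what share falls before 72 hours.

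**The case against.** **The change score already uses baseline, and comparing raw changes is a recognised method.** Both are true. What is missing is baseline as a covariate. PCT clearance is also baseline-relative, so the gap for PCT is narrower than for SOFA, but clearance is not a covariate adjustment.

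**The size is undetermined.** This stands. The cuts shown run from 0.2% to 58% on assumptions alone. The direction is secure, apart from about one degree of freedom; the size is not.

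**A usable baseline is not guaranteed.** This also stands. Section II ties day one to admission, the variable list to admission or enrollment, and both count it among the four days of treatment. Section III (Duration of Treatment) says "HAT will be initiated within 4 hours of enrollment", and nothing states that the day-one SOFA or PCT precedes the first dose. Adjusting for a post-dose value could bias the comparison. The remedy therefore depends on fixing that time point.

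**A reader might infer that the planned comparison is biased.** The documents do not support this. With complete 72-hour data, randomization makes the raw comparison valid. Early deaths leave no 72-hour value, section III stops new data collection after withdrawal (safety data excepted), and it drops patients who withdraw or meet exclusion criteria. That selection would affect ANCOVA just as it affects raw change, so it is a separate limitation and not a result of omitting the covariate.

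**Conclusion.** The point holds as an optional gain in precision on two of the eight secondary outcomes. At equal SDs and correlations from 0.3 to 0.9, the variance of the arm difference falls by 35% down to 5%, so intervals are about 19% to 2.5% narrower. The gain is larger if the SD shrinks by 72 hours, and can be close to nil if it grows. These figures rest on assumed correlations and SD ratios, complete 72-hour data and a roughly linear relation to baseline. The point holds on the ANOVA route and, for SOFA, on the Mann-Whitney route as well.

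It does not extend to the primary outcome: neither the survival comparison nor the sample size of 132 depends on it.

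**What to change.** In section VI:

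1. Make ANCOVA with arm and baseline the principal analysis of 72-hour change in SOFA and in PCT. Use the log scale for PCT if it is skewed, judged on pooled data blind to arm.
2. If SOFA is to be treated as ordinal, say so in advance and use a baseline-adjusted rank test in place of Mann-Whitney on raw change.
3. Define baseline as the value at enrollment before the first dose, and align section II and the variable list with that definition.
4. Keep raw change as descriptive support, and leave PCT clearance as its own listed outcome, so that PCT change has a single principal test.
5. Report by arm the number without a 72-hour value, separating deaths from withdrawals, and add a sensitivity analysis that ranks early deaths worst.

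The cost is a few sentences, with no new outcome, visit or patient, and no extra sample if the day-one sample is drawn before dosing. The downsides are the linearity assumption and about one degree of freedom.

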## **VII. POWER ANALYSIS AND DETERMINATION OF STUDY SIZE:**

Based on published data in patients with necrotizing soft tissue infections, as well as our institutional data, we expect the mortality rate for our control patients to be approximately 20% when no NAT is used. If we anticipate a 78.8% decrease in mortality as observed in the trial by Marik, we would expect to see a decrease in mortality to a rate of 4.24%. Assuming an  $\alpha$  level of 0.05, and 80% power, analysis suggests that we would need a minimum of 66 patients in each of the two study groups for a sample size of 132 participants.

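### Section VI leaves raw-scale ANOVA only when variances differ, which is the wrong trigger for skewed secondary outcomes, and does not fix the fallback test in advance

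*Combined protocol and SAP*

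**What the plan says.** Section VI sets the default: "One-way analysis of variance will be utilized to compare continuous data". With two arms this is the pooled-variance t-test. The only stated departure is "Where heterogeneity of variance is identified, data will be either transformed and analyses rerun, or data will be analyzed using the Mann-Whitney U-Test". Section VI does not name the variance test, its threshold, the transformation, or what decides between transformation and rank test. Skewness and non-normality are not mentioned. Ordinal data go to Mann-Whitney without any trigger and categorical data to chi-square. Tests are two-tailed, and "results of analyses will be considered significant if the resultant P-value is less than or equal to 0.05".

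Section II lists the secondary outcomes, starting with "Duration of vasopressor therapy", and names no test for any of them. Four are plainly continuous: vasopressor duration (recorded in hours), ICU length of stay (days), 72-hour change in procalcitonin, and percent procalcitonin clearance. SOFA change may count as ordinal. The number of wound-related operations is a count, which Section VI does not clearly place.

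**The concern.** Durations such as vasopressor hours and ICU days can be expected to have long right tails, though the documents give no data on this. For such outcomes the choice between raw-scale, log-scale and rank analysis can matter a good deal for power. The plan makes that choice depend on a preliminary test of something else.

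The preliminary test is also not independent of the comparison. A few very long stays in one arm raise both its mean and its spread. The variance test therefore tends to fire in the samples where ANOVA would have rejected, and tends to leave ANOVA in place where long tails in both arms make it weak.

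Each branch answers a different question: a difference in means, a difference on a transformed scale, or a shift in distribution. Under this rule the observed spread decides which question is answered, and where the fallback applies the analyst can still choose between two tests. What is at stake is the power and interpretability of several secondary results.

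**Working it through.** **Inputs from the documents.** 66 per arm, 1:1; two-sided α = 0.05; ANOVA, with transformation or Mann-Whitney if variances differ. **Assumed, because the documents are silent:** outcome shapes and spreads; a mean-based Levene test at 0.05 as the trigger; the logarithm as the transformation. Results are Monte Carlo rejection rates from 10,000 to 20,000 simulated trials per case.

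**1. The plan's own figure.** Section VII assumes 20% against 4.24% mortality and 80% power. The mean rate is (0.20 + 0.0424)/2 = 0.1212, so

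n = [1.960·√(2·0.1212·0.8788) + 0.842·√(0.20·0.80 + 0.0424·0.9576)]² / 0.1576² = (0.9046 + 0.3770)² / 0.02484 ≈ 66.1.

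This is 67 rounded up, against 66 stated; power at 66 is 79.9%. The figure is reproduced to within one patient. It concerns mortality only. No power is stated for any continuous outcome.

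**2. Does unequal variance harm ANOVA here?** With equal arms the pooled squared standard error is [(s₁² + s₂²)/2]·(2/n) = (s₁² + s₂²)/n, the same as the unpooled one. Only the degrees of freedom differ. Simulated null rejection with normal data:

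| SD ratio | ANOVA | Welch | Mann-Whitney |
|---|---|---|---|
| 2 | 5.0% | 4.9% | 6.0% |
| 3 | 5.1% | 4.9% | 6.7% |

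ANOVA holds its level. The Mann-Whitney fallback is slightly worse on the problem it is meant to cure.

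**3. Skewed outcome, no effect.** With identical lognormal distributions in both arms, the rule rejects in 2.1% to 3.1% of trials at log-SD 0.8 to 1.2, and in just under 4% at log-SD 0.5. At log-SD 1.0, Mann-Whitney used throughout is at 4.9%. The rule is conservative.

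**4. Skewed outcome, ratio effect.** The effect is set to give about 80% power on the log scale: δ = σ(1.960 + 0.842)√(2/66) = 0.488σ, a ratio of exp(−0.488σ). Power in %, loss in points:

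| Log-SD σ | Ratio | Fixed Mann-Whitney | Rule, Mann-Whitney fallback | Loss | Fixed log | Rule, log fallback | Loss |
|---|---|---|---|---|---|---|---|
| 0.5 | 0.78 | 77.2 | 71.9 | 5.3 | 79.3 | 73.3 | 6.0 |
| 0.8 | 0.68 | 77.7 | 63.2 | 14.5 | 79.6 | 64.9 | 14.7 |
| 1.0 | 0.61 | 77.2 | 58.2 | 19.0 | 79.6 | 60.5 | 19.1 |
| 1.2 | 0.56 | 77.2 | 55.3 | 21.9 | 79.5 | 57.6 | 21.9 |
| 1.5 | 0.48 | 77.8 | 52.9 | 24.9 | 79.8 | 55.2 | 24.6 |

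With a median-centred variance test, the loss at log-SD 1.5 is about 37 points.

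**5. Other skewed shapes** (rule with Mann-Whitney fallback; power in %, loss in points):

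| Shape | ANOVA | Fixed Mann-Whitney | Rule | Loss v. Mann-Whitney | Loss v. ANOVA |
|---|---|---|---|---|---|
| Exponential, mean ratio 0.6 | 81.9 | 70.7 | 69.1 | 1.6 | 12.8 |
| 30% zeros in both arms, otherwise lognormal (log-SD 1.0), ratio 0.6 | 42.0 | 28.3 | 24.1 | 4.2 | 17.9 |
| The same, with 30% v. 40% zeros | 60.4 | 61.3 | 50.7 | 10.6 | 9.7 |

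For the exponential case a median-centred variance test gives 70.7% under the rule, a loss of 81.9 − 70.7 = 11.2 points against ANOVA. For an additive shift at log-SD 1.0 the loss against Mann-Whitney is 43 to 50 points.

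In every skewed shape tried with a treatment effect, Mann-Whitney fixed in advance matched or beat the rule that falls back on it under the mean-based variance test.

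**The case against.** The strongest reply is that no single figure for the loss can be defended. The documents give no shape, SD or effect for any continuous outcome. A reader might infer from the log-SD 1.0 row that the rule costs about 20 points on skewed outcomes, or at most 20. Neither is supported: the size depends on an assumed lognormal shape with a ratio effect, and steps 4 and 5 show losses from about 2 points to well above 25. This objection stands.

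Nor is Mann-Whitney the best test throughout. In the exponential case plain ANOVA beats it by 81.9 − 70.7 = 11.2 points, and with 30% zeros in both arms by 42.0 − 28.3 = 13.7. Zero vasopressor hours are plausible, because Section III requires sepsis, not shock. A lognormal has no zeros, and zero hours cannot be logged without a further convention. This stands as a caution about the choice of test. It does not rescue the rule, which does worse than both fixed tests in each row of step 5.

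A reader might also infer that the rule manufactures false differences when means agree but spreads differ. That is not a fair charge. With equal means and log-SDs 1.0 and 0.6 the rule rejects in 32.3% of trials, but Mann-Whitney fixed in advance rejects in 57.3%, because it tests a different hypothesis and the medians do differ. With identical distributions the rule under-rejects.

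Finally, it would be too strong to say that most secondary outcomes are right-skewed and pass through this rule. Procalcitonin change can take either sign and clearance cannot exceed 100%, so neither is lognormal. SOFA may already go to Mann-Whitney, and the operation count is unclassified. Of the four plainly continuous outcomes, only vasopressor duration and ICU stay resemble the shapes simulated.

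**Conclusion.** The point holds as a defect in how the rule is specified. Unequal variance is the wrong trigger in a two-arm trial with 66 per arm, skew never triggers a switch, and the choice of test and hypothesis is left to the data.

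Its size is conditional. For a lognormal outcome with a ratio effect and log-SD 0.5 to 1.5, the loss is about 5 to 25 points against the same fallback test fixed in advance, about 19 at log-SD 1.0. Null rejection is about 2% to 4% (log-SD 0.5 to 1.2). For an exponential outcome, or a zero-inflated one with equal zeros in both arms, the loss is about 2 to 5 points against fixed Mann-Whitney and 11 to 18 against fixed ANOVA. These ranges illustrate the cost and are not bounds.

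Only secondary outcomes are affected. Hospital survival is categorical and goes to chi-square, so neither the primary test nor the 66 per arm changes. The amendment is advisable, not critical.

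**What to change.** Delete the variance-triggered switch from Section VI and name one test per continuous outcome before the data are seen. One workable set:

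- Vasopressor duration and ICU stay: Mann-Whitney, with the Hodges-Lehmann difference and its 95% CI.
- Procalcitonin: log 72-hour value compared between arms, adjusted for the log day-1 value. This avoids logging a change or clearance that may be negative. State how it relates to the two procalcitonin outcomes in Section II.
- SOFA change and number of operations: state how each is classed and which single test applies.

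The amended text should admit the downside. Mann-Whitney compares distributions, not means, and has less power than ANOVA for some shapes, for example when many patients in both arms have zero vasopressor hours. If the sponsor expects that shape, or wants a difference in means, a Welch test fixed in advance is a reasonable alternative.

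The cost is two or three sentences. The methods are standard, and no further data or patients are needed. The change does not settle how patients who die enter the duration and 72-hour outcomes; Section VI is silent on that, and it needs its own rule.
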